UM IRB No.: 20211211

NCT05545735

Protocol Date: November 14, 2023

Principal Investigator: [name]., M.S.P.H.

Study Title: The Duration of Antibiotic Therapy for Early VAP (DATE) Trial

Cover Page for Protocol

Sponsor name:	None
ClinicalTrials.gov ID#	NCT05545735
University of Miami IRB#	20211211
Brief title:	The Duration of Antibiotic Therapy for Early VAP (DATE) Trial
Official title of study:	The Duration of Antibiotic Therapy for Early VAP (DATE) Trial: A Surgical Infection Society Multicenter Randomized Clinical Trial of 4 vs. 7 Days of Definitive Antibiotic Therapy for Early Ventilator-Associated Pneumonia in the Surgical Intensive Care Unit
Document date:	November 14, 2023

UM IRB No.: 20211211

NCT05545735

Protocol Date: November 14, 2023

Principal Investigator: [name]., M.S.P.H.

Study Title: The Duration of Antibiotic Therapy for Early VAP (DATE) Trial

I. Protocol Title

The Duration of Antibiotic Therapy for Early VAP (DATE) Trial: A Surgical Infection Society Multicenter Randomized Clinical Trial of 4 vs. 7 Days of Definitive Antibiotic Therapy for Early Ventilator-Associated Pneumonia in the Surgical Intensive Care Unit

II. IRB Review History

Not applicable

III. Hypothesis and Specific Aims

The **hypothesis** of this randomized controlled trial (RCT) is that 4 days of antibiotic therapy, as compared to 7 days, is non-inferior regarding the primary outcome of ventilator-associated pneumonia (VAP) recurrence and superior in decreased antibiotic exposure among surgical intensive care unit (ICU) patients with early (within 2 – 7 days of intubation via endotracheal or tracheostomy tube) VAP. Our **specific aim** is to determine whether 4 days of antibiotic therapy is non-inferior to 7 days of antibiotic therapy for the treatment of early VAP with regards to recurrence and superior with regards to antibiotic exposure time.

IV. Background

The prevalence of multidrug resistant (MDR) pathogens in ICUs worldwide has reached epidemic proportions (1, 2). In some cases, the choice of potential therapy is limited or even nonexistent (3). Antibiotic prescription, through selection pressure, represents the main mechanism by which resistance emerges (4). Limitations in the development of new antibiotics (5) underscores the importance of adherence to the principles of antibiotic stewardship (6).

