VAP is the most common serious infection in mechanically ventilated critically ill patients (7). Approximately one half of antibiotic prescription in the ICU is related to VAP, including prophylactic, empiric, and definitive therapy (8). The development of evidence-based

UM IRB No.: 20211211

NCT05545735

Protocol Date: November 14, 2023

Principal Investigator: [name]., M.S.P.H.

Study Title: The Duration of Antibiotic Therapy for Early VAP (DATE) Trial

algorithms for the rational use of antibiotics in the management of patients with both suspected and confirmed VAP is pivotal to decreasing the emergence of MDR pathogens.

Shortening the duration of antimicrobial therapy for VAP represents one strategy to curtail the emergence of MDR pathogens. Although prior guidelines recommended a treatment course of 8 – 14 days (9), newer guidelines recommend a treatment course of 7 days (10, 11) and data show that both clinical and microbiological resolution of infection typically occur much sooner (12, 13). In one study of ICU patients ventilated for > 5 days who developed VAP, 8 days of antimicrobial therapy was equally as effective as 15 days, provided VAP was not caused by a non-lactose fermenting gram negative bacillus (14). Favorable results following courses of therapy < 8 days have been reported, albeit in small uncontrolled series (15).

One subset of patients for whom a decreased duration of antimicrobial therapy may be particularly effective is those who develop VAP \leq 7 days after intubation (i.e., early VAP). Early VAP comprises the majority of cases of pneumonia diagnosed in the ICU (16). Furthermore, as compared to patients who develop late VAP, patients who develop early VAP are more likely to be infected with community-acquired pathogens sensitive to narrow spectrum antibiotics (16).

Finally, nearly all cases of early VAP caused by sensitive pathogens demonstrate microbiological resolution after relatively short (i.e., 3 – 5 day) courses of therapy (12). Therefore, we have designed this multicenter randomized controlled trial in partnership with the Surgical Infection Society to determine whether a shorter course of antibiotic therapy (i.e., 4 days) is non-inferior as longer therapy (i.e., 7 days) for the treatment of early VAP in critically ill surgical patients regarding recurrences and superior regarding antibiotic exposure.

UM IRB No.: 20211211

NCT05545735

Protocol Date: November 14, 2023

Principal Investigator: [name]., M.S.P.H.

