The total required sample size for this study is **458 patients**. Assumptions for the power analysis include non-inferiority for VAP recurrence and superiority for antibiotic-free days in the intervention group, 3 planned analyses of the data with O'Brien-Fleming spending function with binding futility boundaries, 25% recurrence rate in the control group (14), and 6 enrolling centers with an average cluster size of 10. To detect a 10% difference in outcomes between groups with 80% power and assuming a 10% dropout rate, a total sample size of 458 patients is required for this study. Sample size will be recalculated at each interim analysis with better estimates based on accrued patients. The planned analyses will take place after enrollment of 150, 300, and all patients.

VII. Study-Wide Recruitment Methods

This is a multicenter randomized controlled trial. We have partnered with the Surgical Infection Society to aid in recruitment of interested centers for participation in the study. The recruitment methods for individual subjects to participate in the study will be uniform across all centers. A member of the research team at each center will screen all patients in their respective surgical ICUs by reviewing the medical record of each patient in the ICU for eligibility based on the inclusion and exclusion criteria listed in *Section V* (above). Screening will occur daily during the study period. We will be requesting a waiver of the requirement for written authorization

UM IRB No.: 20211211

NCT05545735

Protocol Date: November 14, 2023

Principal Investigator: [name]., M.S.P.H.

Study Title: The Duration of Antibiotic Therapy for Early VAP (DATE) Trial

from patients to access their health records due to the nature of the study. Please see further documentation in *Section XXXII* (below).

VIII. Study Timeline

Each individual patient enrolled in the study will be followed for 30 days or until hospital discharge, whichever occurs first. We will also review patient charts at hospital discharge to determine overall hospital length of stay and overall mortality, in addition to 30-day outcomes. We expect all subjects to be enrolled within the first 2 years of study across all centers, with full data analysis completed at 3 months after study completion.

IX. Study Endpoints

A) Primary Outcomes

- a.** VAP recurrence within 30 days
 - i.** VAP recurrence = VAP occurring 2 – 14 days following completion of initial therapy

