will be captured as clinical outcomes and do not need to be reported as SAEs unless felt related to study procedures.

XI. Data and Specimen Banking

There will be no specimen banking for this study.

XII. Data Management

All data will be collected on the attached case report form (CRF) and then input by study personnel at each individual site into the University of Miami REDCap electronic data management system. Each site PI will be responsible for keeping a secure file linking the patient medical record number (MRN) to their study ID in the event that additional information is required for study analysis, which will be destroyed at the conclusion of the study. All data will be entered into REDCap in a de-identified manner, using only the study ID, without including any personal identifying information. Data analysis will be performed by [name], PhD. [name] is a tenured Professor of Surgery and Public Health at the University of Colorado Denver and the Colorado School of Public Health, where she is also the Associate Director of the NIH-funded T32 postdoctoral research fellowship in trauma surgery, and statistical consultant to the Ernest E. Moore Shock Trauma Center at Denver Health Medical Center. Additionally, she is the former Statistical Editor for the *Journal of Trauma and Acute Care Surgery*, with over 30 years' experience in injury-related research, particularly in critically ill and injured patients.

Three equally spaced analyses (two interim and one final) will be conducted for all outcomes, using the O'Brien-Fleming alpha spending function. Data analyses will be performed using SAS v9.4 (SAS Inc., Cary, NC). Randomization will occur at the hospital level in blocks of 20. Data will be analyzed using an intention-to-treat strategy (i.e., data of patients randomized to receive 4 days of antibiotic therapy will be analyzed as belonging to this group even if they receive longer courses) and a per-protocol strategy (i.e., crossovers and protocol violations

UM IRB No.: 20211211

NCT05545735

Protocol Date: November 14, 2023

Principal Investigator: [name]., M.S.P.H.

Study Title: The Duration of Antibiotic Therapy for Early VAP (DATE) Trial

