excluded). Data will be expressed as median (interquartile range) or frequency (%). Normality of continuous variables will be assessed by visual inspection of histograms. Differences in the means of continuous normally distributed variables will be assessed using Student's t-test or ANOVA. Differences in the medians of non-normally distributed continuous variables will be assessed using the Wilcoxon rank sum or Kruskal-Wallis tests. Proportions will be compared using the chi-squared or Fischer's exact test, as appropriate. Univariate analysis of categorical outcomes will be expressed as the relative risk with 95% confidence intervals, with standard errors adjusted for intra-center clustering. A generalized estimating equation or linear mixed model (with appropriate transformation of outcome variables to approximate normality, if needed) will be fit to address possible confounding if randomization fails to assure equitable distribution. Baseline variables associated with randomization status at the $p < 0.25$ level by univariate analysis will be added to the model using a stepwise selection method. The overall contribution of the fitted model to predicting variability in the outcome of interest will be assessed using the likelihood ratio chi-squared test. The alpha error level is defined at 0.05, with statistical significance at $p < 0.05$. No adjustment for multiplicity of outcomes will be done as this is an exploratory (rather than confirmatory) trial, and all hypotheses are pre-planned. Adjustment for multiple comparisons in pre-planned hypotheses leads to more type II errors (19, 20).

XIII. Provisions to Monitor the Data to Ensure the Safety of Subjects

As mentioned previously (see *Section X*), a DSMB will be convened. The DSMB will meet after each planned interim analysis, review data collected across all sites, and submit a written report to the overall study PI, who will submit the report to the IRB. Data analysis will be performed by [name], as mentioned above (see *Section XII*).

Data will be monitored daily at each site and any adverse events will be reported to the site PI per local IRB regulations. Efficacy and safety data will be collected on CRFs and inputted into REDCap by study personnel at each site. The study will be terminated early if there are

UM IRB No.: 20211211

NCT05545735

Protocol Date: November 14, 2023

Principal Investigator: [name]., M.S.P.H.

Study Title: The Duration of Antibiotic Therapy for Early VAP (DATE) Trial

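### The main question is non-inferiority on VAP recurrence, but Section XII names only an equality test and gives no margin or confidence limit to decide it

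*Combined protocol and SAP*

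**What the plan says.** - **Objective.** Section III hypothesises that 4 days "is non-inferior regarding the primary outcome of ventilator-associated pneumonia (VAP) recurrence". Section IV repeats that the shorter course "is non-inferior as longer therapy (i.e., 7 days) for the treatment of early VAP". Section IX lists recurrence first among the primary outcomes.
- **Sample size (Section VI).** "Assumptions for the power analysis include non-inferiority for VAP recurrence and superiority for antibiotic-free days in the intervention group". The only effect size is in the phrase "To detect a 10% difference in outcomes between groups with 80% power and assuming a 10% dropout rate", which leads to 458 patients. The control recurrence rate is taken as 25%. The design has three looks with O'Brien-Fleming spending and binding futility boundaries: "The planned analyses will take place after enrollment of 150, 300, and all patients".
- **Analysis (Section XII).** "Three equally spaced analyses (two interim and one final) will be conducted for all outcomes, using the O'Brien-Fleming alpha spending function". "Data will be analyzed using an intention-to-treat strategy", and a per-protocol analysis is planned as well. For the test itself: "Proportions will be compared using the chi-squared or Fischer's exact test, as appropriate". Categorical outcomes are also to be summarised as relative risks with 95% intervals, adjusted for clustering by center. A GEE or mixed model is fitted only if randomization leaves imbalance. Alpha is 0.05, with no statement of one- or two-sided.
- **Early stopping (Section XIII).** Efficacy stopping depends on the DSMB judging that one group clearly benefits.

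The available text contains no non-inferiority margin, null value or decision rule. The DSMB Charter and a few parts of the protocol were not available for this check.

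**The concern.** A chi-squared or Fisher test has equality of the two rates as its null hypothesis. A significant result shows a difference, and a non-significant one shows only that a difference was not demonstrated. Neither outcome says that the 4-day arm is worse by no more than a tolerable amount.

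The relative-risk interval is a suitable tool, but it answers a non-inferiority question only against a fixed limit. Section VI's 10% might be that limit. However, it is worded as a difference to detect, it is not said to be absolute or relative, and Section XII never uses it. Section XII also reports a ratio, so an absolute 10 points would have to be converted, and the conversion depends on the control rate.

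The limit, its scale, the sidedness and the deciding analysis set could therefore all be settled after the data are seen. The interim boundaries for recurrence are also undefined, because an efficacy or futility boundary needs a null value.

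**Working it through.** **Inputs.** From Section VI: 458 patients, 10% dropout, 25% control rate, 10% difference, 80% power. From Section XII: alpha 0.05 and 95% intervals. Assumed: 1:1 allocation. For the illustrations, also a single look and no clustering, since no intra-center correlation is given.

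**1. Does 458 show that the 10% is a margin?** For an absolute margin of 0.10 with 25% in both arms, n per arm = (z_alpha + z_beta)² × 2 × 0.25 × 0.75 / 0.10².

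- One-sided 0.025: (1.960 + 0.842)² × 0.375 / 0.01 = 294.3, so 295 per arm or 590. Dividing by 0.9 for dropout gives 656. Three looks with binding futility bring it to about 698.
- One-sided 0.05: (1.645 + 0.842)² × 0.375 / 0.01 = 231.8, so 232 per arm or 464. Dropout gives 516, and three looks about 555.

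Neither reproduces 458 with all stated inputs. Two calculations come within 3%. One is non-inferiority at one-sided 0.05 with no allowance for dropout or looks (464). The other is a one-sided 0.05 calculation to detect 25% vs 15%, with looks and dropout (about 466 to 471). The sample size does not settle what the 10% means.

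**2. Evaluable patients.** 458 × 0.9 = 412, or 206 per arm.

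**3. Same data, different readings.** Fix 52/206 (25.2%) recurrences on 7 days.

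- Risk-difference upper limit: d + 1.96 × √[p₄(1−p₄)/206 + p₇(1−p₇)/206].
- Relative-risk upper limit: RR × exp(1.96 × √[1/x₄ − 1/206 + 1/52 − 1/206]).
- Ten points at a 25% control rate is RR 0.35/0.25 = 1.40. At 15% it is 1.67, and at 30% it is 1.33.

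| 4-day count | Upper limit, difference | Upper limit, RR | Chi-squared p |
|---|---|---|---|
| 39 | 1.7 points | 1.083 | 0.12 |
| 52 | 8.4 points | 1.394 | 1.00 |
| 53 | 8.9 points | 1.418 | 0.91 |
| 55 | 9.9 points | 1.466 | 0.74 |
| 56 | 10.4 points | 1.490 | 0.65 |
| 70 | 17.5 points | 1.822 | 0.052 |
| 71 | 18.0 points | 1.845 | 0.041 |

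The largest passing count is 55 for 10 absolute points, 52 for RR 1.40, and 39 if the 10% is relative (RR 1.10). Counts of 53 to 55 get opposite verdicts under the first two rules. Chi-squared remains non-significant up to 70, where an excess of 17.5 points is not excluded.

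**4. Chance of passing (exact binomial enumeration, 206 per arm, two-sided 95% interval).**

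- True rates 25% and 25%: 65% (10 points), 50% (RR 1.40), 8% (RR 1.10). The 10-point and RR 1.40 verdicts differ in 14.7% of trials.
- True rates 35% on 4 days and 25% on 7 days: 2.5% pass the 10-point rule. Chi-squared is non-significant in 39.6%.

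**5. Power under a 10-point rule.** The standard error is √(2 × 0.1875/206) = 0.0427.

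- One-sided 0.025: Φ(0.10/0.0427 − 1.960) = Φ(0.384) = 65%.
- One-sided 0.05: Φ(0.699) = 76%.
- All 458 evaluable (229 per arm): 70% and 80%.

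**The case against.** **The 10% is plainly the margin.** It follows a list of power assumptions that opens with non-inferiority for recurrence, and at one-sided 0.05 with all 458 evaluable it gives close to 80% power. This is a reasonable guess at intent, and the fix allows for it. But a detect-a-difference calculation fits about as well, the scale is not stated, and Section XII does not use the figure.

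**The equality test is never designated as the primary recurrence analysis.** It sits in a general list of tests, and the relative-risk interval follows it. That is true, but it is still the only test the plan names for a proportion, and the interval comes with no limit.

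**A relative 10% is not credible.** RR 1.10 would need 3,710 to 4,710 per arm before dropout. This stands. The dispute that matters is 10 points against RR 1.40, and those two alone give opposite verdicts.

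**The 40% false-pass figure presumes a misuse the plan does not state.** This also stands. The plan neither says nor excludes that a non-significant result would be read as non-inferiority. The figure is a conditional risk, and the conclusion does not depend on it.

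**The trial is called exploratory.** Section XII uses that word to justify not adjusting for multiple outcomes, and the same sentence says all hypotheses are pre-planned. A pre-planned non-inferiority hypothesis needs a pre-planned criterion.

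**The exact counts ignore the three looks and clustering.** They do. They show how far the readings diverge and are not the trial's actual thresholds.

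**Conclusion.** The concern holds, and the text must be corrected. Carried out as written, Section XII does not answer the trial's main question: its named test addresses equality, and its interval has nothing to be compared with. The two plausible readings of the 10% differ by 15 percentage points in the chance of success when the arms are truly equal (65% vs 50%), and they disagree in about one trial in seven. These figures assume 206 evaluable per arm, 1:1 allocation, a 25% control rate, one look, a two-sided 95% interval and no clustering. That the decision rule is absent from Sections VI and XII does not depend on those assumptions. A margin stated in the DSMB Charter or another part not seen here cannot be ruled out, but Section XII as written would still not apply it.

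**What to change.** In Section XII, make a confidence-limit rule the primary analysis of recurrence. Non-inferiority is declared only if the upper confidence limit for the 4-day minus 7-day risk difference lies below the margin, at the O'Brien-Fleming level for that look and with hospital accounted for by a named method. The sponsor should:

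- confirm the margin, either the 10% as absolute percentage points or an explicit relative-risk limit if the relative risk is kept as primary;
- state the one-sided alpha;
- state, with a reason, how the intention-to-treat and per-protocol analyses enter the decision, including what follows if they disagree;
- add a matching sentence to Section VI that calls the figure a margin.

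All of this should be fixed before the first look at 150 patients, not at the interim sample-size recalculation. Chi-squared and Fisher tests can stay for secondary proportions.

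The cost is text only, with no new data items. The downside to disclose is power. With an absolute 10-point margin and 25% in both arms, 458 enrolled less 10% dropout gives about 65% at one-sided 0.025 or 76% at one-sided 0.05, before clustering, interim looks and futility bounds. The stated 80% needs restating under the chosen rule.

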Study Title: The Duration of Antibiotic Therapy for Early VAP (DATE) Trial

V. Inclusion and Exclusion Criteria

A) Inclusion Criteria

- a.** Surgical patient
- b.** Early VAP, defined as VAP occurring within 2 – 7 days of intubation (via endotracheal or tracheostomy tube) (9). VAP will be defined according to local institutional protocol.
- c.** Hospital length of stay (LOS) \leq 10 days at the time of VAP diagnosis.
- d.** Patients are willing to provide informed consent or their Legally Authorized Representative (LAR) is willing to provide informed consent on their behalf when the patient is unable (i.e., cognitively impaired from sedation on a ventilator).

B) Exclusion Criteria

- a.** Age $<$ 18 years
- b.** Prior episode of VAP for the index admission
- c.** VAP caused by any of the following pathogens:
 - i.** Methicillin-resistant *Staphylococcus aureus* (MRSA)
 - ii.** Vancomycin-intermediate *Staphylococcus aureus* (VISA)
 - iii.** *Pseudomonas aeruginosa*
 - iv.** Vancomycin-resistant *Enterococcus* (VRE)
 - v.** *Acinetobacter baumanii*
 - vi.** *Stenotrophomonas maltophilia*
 - vii.** Carbapenem-resistant *Enterobacteriaceae* (CRE)
 - viii.** Extended-spectrum beta lactamase-producing gram-negative bacilli
- d.** Causative pathogen not sensitive to choice of initial empiric antibiotic
- e.** Antibiotic therapy for \geq 5 of the last 10 days preceding VAP diagnosis
- f.** Septic shock, defined as evidence of tissue hypoperfusion after adequate volume expansion, due to infection, and requiring \geq 1 vasopressor (17)

UM IRB No.: 20211211

NCT05545735

Protocol Date: November 14, 2023

Principal Investigator: [name]., M.S.P.H.

Study Title: The Duration of Antibiotic Therapy for Early VAP (DATE) Trial

- g.** Current or recent (within 30 days) use of immunosuppressive medications
- h.** LOS \geq 72 hours at a transferring facility
- i.** Pregnancy or lactation
- j.** Legal arrest or incarceration
- k.** Moribund state in which death is imminent
- l.** ECMO (Extracorporeal membrane oxygenation)
- m.** Extubation prior to randomization

VI. Number of Subjects

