- b.** Antibiotic-free days within 30 days

B) Secondary Outcomes

- a.** Antibiotic exposure
 - i.** Days of antibiotics
 - ii.** Antibiotic days (defined as the product of days of antibiotics and number of antibiotics per day)
- b.** Clinical improvement, measured using daily CPIS_{clinical} score while enrolled in the study
- c.** VAP relapse = recurrent VAP caused by initial pathogen (if culture data available), occurring 2 – 14 days following completion of initial therapy
- d.** 30-day Ventilator-free days

UM IRB No.: 20211211

NCT05545735

Protocol Date: November 14, 2023

Principal Investigator: [name]., M.S.P.H.

Study Title: The Duration of Antibiotic Therapy for Early VAP (DATE) Trial

- e. Empyema
- f. Need for tracheostomy
- g. Non-pulmonary infections
- h. 30-day ICU-free days
- i. Hospital LOS
- j. In-hospital Mortality

X. Procedures Involved

This is a multicenter, randomized, clinical trial. The trial will be reported in accordance with the recommendations of the CONSORT statement (18). IRB approval will be obtained. All subjects, or their legally authorized representatives, will provide written consent for study participation. The trial is registered with the US National Institutes of Health (ClinicalTrials.gov Identifier #NCT05545735).

Screening will occur daily by study personnel. Eligible patients will be approached as soon as possible after inclusion criteria are met (i.e., 1 – 3 days prior to randomization). Randomization will occur using a computer-generated block pattern no later than the end of the fourth day of appropriate antibiotic therapy. Randomization will occur at the hospital level in blocks of 20.

Empiric antibiotic therapy will be instituted as soon as possible following diagnosis of suspected pneumonia by the clinical team. The default antibiotic will be based on the local institutional antibiogram and practice. Pre-existing treatment for a non-pulmonary infection with at least one antibiotic that has appropriate activity against the VAP pathogen may be substituted for the default antibiotic. Once sensitivity data become available, therapy may be de-escalated to a more narrow-spectrum agent, as indicated.

The default duration of antibiotic therapy will be determined by study group assignment; the treatment team will be asked to adhere to study group assignment whenever possible. However, the treatment team may choose to extend the duration of antibiotic therapy based on

UM IRB No.: 20211211

NCT05545735

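### Section XII ignores the hospital strata used in randomization and names no estimator for its center-adjusted relative-risk interval; with 6 centers, the common choice under-covers

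*Combined protocol and SAP*

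**What the plan says.** **Randomization.** Section X says "Randomization will occur using a computer-generated block pattern", and both Section X and Section XII add "Randomization will occur at the hospital level in blocks of 20". The intention-to-treat text in Section XII speaks of patients being randomized to a duration. The natural reading is therefore patient-level randomization stratified by hospital, with both arms in every hospital.

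**Tests.** In Section XII, "Proportions will be compared using the chi-squared" or an exact test. Normally distributed outcomes get a t-test or ANOVA, and differences in non-normal outcomes "will be assessed using the Wilcoxon rank sum or Kruskal-Wallis tests". None of these has a hospital stratum or term.

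**Interval.** Categorical outcomes also get a "relative risk with 95% confidence intervals, with standard errors adjusted for intra-center clustering". The standard-error method, the reference distribution and any small-sample correction are not given.

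**Models.** A GEE or mixed model "will be fit to address possible confounding if randomization fails to assure equitable distribution". It is conditional on imbalance, and hospital is not named as a stratum or covariate.

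**Centers.** Section VI assumes "6 enrolling centers with an average cluster size of 10" and a total of 458 patients.

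**The concern.** When randomization is blocked within hospital, the matching analysis compares arms within hospital and combines the results. Section XII does not do this. Its one center adjustment can be carried out in ways that err in opposite directions:

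- A center-clustered sandwich estimates the variance from only as many independent totals as there are centers. With 6 centers and a normal quantile, the interval is too narrow.
- A design-effect inflation treats centers as if each held one arm. Both arms share each center here, so the interval is too wide.

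Section XII yields a p-value and an interval for the same outcome, including VAP recurrence, which is a primary outcome. If the two are built on different variances they can conflict in the report, and the plan does not say which governs. The choice of estimator would also be made after data have accrued.

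**Working it through.** **Inputs from the documents.** 6 centers, average cluster size 10, 458 patients, 10% dropout, 25% control recurrence (Section VI); blocks of 20 within hospital (Sections X and XII). The plan states no ICC, design effect or coverage, so it has no figure of its own for the interval to reproduce.

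**Assumptions.** ICC 0 to 0.10. Center sizes equal, mildly unequal (95/85/75/65/50/42) or strongly unequal (150/100/70/45/27/20). No treatment effect unless stated.

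**1. Center count.** 6 × 10 = 60, not 458. 458/6 = 76.3 patients per center, or 458/10 = 45.8, about 46 centers of 10. Evaluable patients: 458 × 0.9 = 412.

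**2. Sandwich with z, closed form.** With G equal centers, the uncorrected variance estimate is about (G−1)/G times a chi-square(G−1)/(G−1) multiple of the true variance. Coverage of a nominal 95% interval is then P(|t(G−1)| < 1.96 × √((G−1)/G)). No ICC is needed.

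| Centers | Coverage |
|---|---|
| 6 | 86.6% |
| 10 | 90.4% |
| 20 | 92.9% |
| 46 | 94.1% |

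**3. Simulation.** 412 patients, 25% events in both arms, permuted blocks of 20 within center, beta-binomial center rates, interval on log RR. Ranges are over ICC 0-0.10.

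| Method | Equal | Mild split | Strong split |
|---|---|---|---|
| Sandwich, z | 86-87% | 85-87% | 83-85% |
| Variance × G/(G−1), t on 5 df | 94-95% | 94-95% | 93-94% |
| Mantel-Haenszel by hospital | 95% | 95% | 95% |
| Sandwich excludes 1, chi-squared p > 0.05 | 9-10% | 9-11% | 11-13% |

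The correction replaces the multiplier 1.96 by 2.571 × √(6/5) = 2.82, so the interval on the log scale is 2.82/1.96 = 1.44 times as wide. With 46 centers of 9, the uncorrected sandwich covers about 94.5%. The stratified interval and the CMH test disagree in about 0.2% of null trials.

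**4. Other readings of the adjustment.**
- Design effect with cluster size 10, 1 + 9 × ICC: 1.09, 1.18 and 1.45 for ICC 0.01, 0.02 and 0.05. Coverage is 96.0-96.6%, 96.8-97.3% and 98.3-98.6%.
- Design effect with the roughly 69 evaluable patients per center that 6 centers imply: above 99.8% at ICC 0.02 or more.
- Model-based standard errors from an exchangeable GEE, 6 centers, normal quantile: 95-96% at ICC 0.01, 0.05 and 0.10 (600 trials each, so less precise).

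**5. Leaving strata out of the tests.** Chi-squared type I error is about 4-5%, and falls to about 4.1% at ICC 0.10. At 25% vs 15%, CMH gains 0.9-1.5 power points at ICC 0.05 and 1.7-3.4 at ICC 0.10, depending on how the effect is modeled. For example, with equal centers, a constant difference and ICC 0.10, power is 69.9% vs 73.3%. For a continuous outcome near 80% power, van Elteren gains 0.6-0.7 points over Wilcoxon at ICC 0.05 and 1.4-1.5 at ICC 0.10.

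**6. If the effect varies by center.** Assumed SD of log RR across centers, ICC 0.05; coverage of the average effect:

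| SD | Mantel-Haenszel | Corrected, t on 5 df |
|---|---|---|
| 0.15 | 93-94% | 93-95% |
| 0.3 | 84-87% | 91-94% |
| 0.4 | 77-80% | 90-94% |

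**The case against.** **The method is not named.** A reader might infer that the planned interval is too narrow. The documents do not support that. Under-coverage belongs to one common reading, while other readings are near nominal or too wide. What stands is that the plan leaves open a choice that moves coverage from about 83% to over 99%.

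**Six may not be the real number.** It is a planning assumption, it conflicts with cluster size 10 and N = 458, and centers were still being recruited through the Surgical Infection Society. The text under Section XXI (Setting) was not in the copy reviewed, so a site list there could not be checked. This stands as a limit on the size of the problem. Even so, 10 or 20 centers give only 90.4% or 92.9% under the sandwich reading.

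**Ignoring strata might be taken to inflate type I error or to cause the narrow interval.** It does neither. The tests are valid, and the narrowness comes from having few clusters. The case for stratifying is agreement between test and interval, plus a little power.

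**It does not touch the non-inferiority decision directly.** A reader might take the 9-13% disagreement as a false non-inferiority rate. It is not. Section VI gives a 10% difference, which reads as absolute, and states no margin on the relative-risk scale. Excluding RR = 1 is therefore not the non-inferiority test. The demonstrated harm is a conflicting p-value and interval.

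**Mantel-Haenszel is not safe either.** It assumes a common effect, yet "VAP will be defined according to local institutional protocol" and the default antibiotic is also chosen locally. With equal centers and ICC 0.05, the uncorrected sandwich covers 85.0% at SD 0.3 against 86.6% for Mantel-Haenszel, and 83.9% against 79.9% at SD 0.4. This stands, and it is why the corrected clustered interval should be shown beside the stratified one.

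**Conclusion.** The point holds as a gap in specification with a conditional numerical consequence. Hospital strata exist in the randomization and are absent from every comparison in Section XII; by itself this costs about 1-3 power points at assumed ICC 0.05-0.10 and does not make any test invalid. If the unspecified adjustment is a center-clustered sandwich with z = 1.96 and there are 6 centers, a nominal 95% interval covers about 83-87%. That result does not depend materially on the ICC, but does depend on how unequal the centers are. It rests on patient-level randomization within hospital, which the wording supports without stating outright. It is worth correcting before analysis. Confidence is medium, because neither the estimator nor the center count is settled in the documents.

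**What to change.** In Section XII:

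- Analyze by randomization stratum. For recurrence, use CMH/Mantel-Haenszel or stratified Miettinen-Nurminen, with the interval on the absolute risk-difference scale for the non-inferiority question. For antibiotic-free days, use van Elteren. Put hospital as a fixed effect in any model.
- If a center-clustered interval is reported, name a small-sample-corrected variance with t on (centers − 1) df, and show it alongside the stratified result. If the authors keep the clustered interval as the main one, naming that correction is the minimum change.

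In Section VI, reconcile the number of centers and the cluster size with 458 patients.

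**Cost.** Wording and a few lines of SAS; no new data. The stratified interval is wider than the uncorrected sandwich: the median factor on RR is 1.39 against 1.32 (equal centers, ICC 0.05), and 1.49 for the corrected t interval with no heterogeneity. The stratified result carries a common-effect assumption. With strongly unequal centers the simple t correction still reaches only about 93-94%.
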